4. PATIENT SELECTION

This study can fulfill its objectives only if appropriate patients are enrolled. The following eligibility criteria are designed to select patients for whom participation in the study is considered appropriate. All relevant medical and non-medical conditions should be taken into consideration when deciding whether a particular patient is suitable for this protocol.

4.1. Inclusion Criteria

Patient eligibility should be reviewed and documented by an appropriately qualified member of the investigator's study team before patients are included in the study.

Patients must meet all of the following inclusion criteria to be eligible for enrollment into the study:

1. Cytogenetic or PCR-based diagnosis of Ph+ CML or BCR-ABL1+ if Ph- (from initial diagnosis). NOTE: Ph- CML patients will not count towards the 150 patients for primary and secondary analyses, which include Ph+ CML patients only.

NOTE: All patients must have screening bone marrow (BM) cytogenetic analysis with conventional G banding performed within 30 days prior to study entry (unless CML disease status is proven to be MMR by quantitative reverse transcription polymerase chain reaction [qRT-PCR]). Examination of at least 20 metaphases is required.

2. Prior treatment with 1 or more TKIs for CML.
3. Any CML phase, as long as the patient is resistant to, intolerant of, or otherwise not appropriate for treatment with imatinib, dasatinib and/or nilotinib.

4. Eastern Cooperative Oncology Group (ECOG) Performance Status of 0 or 1 for CP patients, or 0, 1, 2, or 3 for 4th line CP (and beyond) and AP/ BP patients.
5. Adequate bone marrow function:
 - For 2nd and 3rd line CP CML patients:
 - Absolute neutrophil count $>1000/\text{mm}^3$ ($>1 \times 10^9/\text{L}$).
 - Platelets $\geq 75,000/\text{mm}^3$ ($\geq 75 \times 10^9/\text{L}$) absent any platelet transfusions during the preceding 14 days.
 - For 4th line CP and AP/BP CML patients:
 - Absolute neutrophil count $>500/\text{mm}^3$ ($>0.5 \times 10^9/\text{L}$).
 - Platelets $\geq 50,000/\text{mm}^3$ ($\geq 50 \times 10^9/\text{L}$) absent any platelet transfusions during the preceding 14 days.
6. Adequate hepatic and renal function:
 - AST/ALT $\leq 2.5 \times$ the upper limit of normal (ULN) or ALT/AST $\leq 5 \times$ ULN if attributable to liver involvement of leukemia.
 - Total bilirubin $\leq 1.5 \times$ ULN (unless the bilirubin is principally unconjugated and there is a strong suspicion of subclinical hemolysis (e.g. chronic hemolysis without clinical symptoms), or the patient has documented Gilbert's Disease);
 - Alkaline phosphatase $\leq 2.5 \times$ ULN.
 - Creatinine $\leq 1.5 \times$ ULN or estimated creatinine clearance (CrCL) $\geq 60 \text{ mL/min}$ as calculated using the standard method for the institution.
7. Able to take daily oral tablets.
8. Age ≥ 18 years.
9. Evidence of a personally signed and dated informed consent document indicating that the patient (or a legally acceptable representative/legal guardian) has been informed of all pertinent aspects of the study.
10. Patients who are willing and able to comply with scheduled visits, treatment plan, laboratory tests, and other study procedures.

11. Male and female patients of childbearing potential must agree to use two highly effective methods of contraception throughout the study and for at least 28 days after the last dose of assigned treatment. A patient is of childbearing potential if, in the opinion of the investigator, he/she is biologically capable of having children and is sexually active.

4.2. Exclusion Criteria

Patients presenting with any of the following will not be included in the study:

1. Participation in other studies involving investigational drug(s) (Phase 1-4) within 14 days or 3 half-lives (whichever is longer) prior to the first dose of bosutinib.
2. Prior bosutinib or ponatinib exposure.
3. Prior hydroxyurea or anagrelide exposure within 72 hours of the baseline CML disease assessment.
4. Known T315I or V299L mutation in BCR-ABL1.
5. Clinically active leptomeningeal leukemia. Patients must be free of central nervous system (CNS) involvement for a minimum of 2 months.
6. Hypersensitivity to the active substance or to any of the following excipients: Microcrystalline cellulose (E460), Croscarmellose sodium (E468), Poloxamer 188, Povidone (E1201), Magnesium stearate (E470b), Polyvinyl alcohol, Titanium dioxide (E171), Macrogol 3350, Talc (E553b), Iron oxide red (E172).
7. Pregnant or breastfeeding females.
8. Males and females of childbearing potential who are unwilling or unable to use two highly effective methods of contraception as outlined in this protocol for the duration of the study and for at least 28 days after last dose of investigational product.
9. Other severe acute or chronic medical or psychiatric condition, including recent (within the past year) or active suicidal ideation or behavior or laboratory abnormality that may increase the risk associated with study participation or investigational product administration or may interfere with the interpretation of study results and, in the judgment of the investigator, would make the patient inappropriate for entry into this study.
10. Patients who are investigational site staff members directly involved in the conduct of the trial and their family members, site staff members otherwise supervised by the Investigator, or patients who are Pfizer employees directly involved in the conduct of the trial.

4.2.1. Philadelphia Chromosome Negative (Ph-) CML Patients

Patients whose CML is BCR-ABL1 positive and Philadelphia chromosome negative (Ph-) will be permitted to enroll. These patients will be in addition to, and not contribute to analysis of, the approximately 150 Ph+ CML patients planned for this study. Due to the lack of data on and treatment options available for this small subset of CML patients, they will be classified and analyzed in a separate, stand-alone cohort. Patients must meet all other eligibility criteria based on their stage of disease, and will be treated in an identical manner as Ph+ CML patients. However, due to their lack of the Ph chromosome, they will be followed for hematologic and molecular response only, as well as safety.

- Treatment with bosutinib may result in a clinically significant decline in renal function in CML patients. A decline over time in estimated glomerular filtration rate (eGFR) has been observed in CML patients with bosutinib treatment. It is important that renal function is assessed prior to bosutinib treatment and closely monitored during therapy, with particular attention in those patients who have preexisting renal compromise or in those patients exhibiting risk factors for renal dysfunction, including concomitant use of medicinal products with potential for nephrotoxicity such as diuretics, angiotensin converting enzyme (ACE) inhibitors, angiotensin receptor blockers and nonsteroidal anti-inflammatory drugs (NSAIDs). Bosutinib exposures were increased in patients with moderately and severely impaired renal function. Dose reduction is recommended for patients with moderate or severe renal impairment.

4.4. Life Style Guidelines

In this study, fertile male patients and female patients who are of childbearing potential will receive bosutinib, which has been associated with demonstrated teratogenicity/fetotoxicity. Subjects who are, in the opinion of the investigator, sexually active and at risk for pregnancy with their partner(s) must agree to use 2 methods of highly effective contraception throughout the study and for at least 28 days after the last dose of investigational product.

The investigator or his or her designee, in consultation with the patient, will confirm that the patient has selected 2 appropriate methods of contraception for the individual patient and his/her partner(s) from the list of permitted contraception methods (see below) and will confirm that the patient has been instructed in their consistent and correct use. At time points indicated in the Schedule of Activities, the investigator or designee will inform the patient of the need to use 2 highly effective methods of contraception consistently and correctly and document the conversation, and the patient's affirmation, in the patient's chart. In addition, the investigator or designee will instruct the patient to call immediately if 1 or both of the selected contraception methods is discontinued or if pregnancy is known or suspected in the patient or partner.

Highly effective methods of contraception are those that, alone or in combination, result in a failure rate of less than 1% per year when used consistently and correctly (i.e., perfect use) and include:

1. Established use of hormonal methods of contraception associated with inhibition of ovulation (eg, oral, inserted, injected, implanted, transdermal), provided the patient or male patient's female partner plans to remain on the same treatment throughout the entire study and has been using that hormonal contraceptive for an adequate period of time to ensure effectiveness
2. Correctly placed copper containing intrauterine device (IUD).

3. Male condom or female condom used WITH a separate spermicide product (ie, foam, gel, film, cream, or suppository). For countries where spermicide is not available or condom plus spermicide is not accepted as highly effective contraception, this option is not appropriate.
4. Male sterilization with absence of sperm in the post-vasectomy ejaculate.
5. Bilateral tubal ligation/ bilateral salpingectomy or bilateral tubal occlusive procedure (provided that occlusion has been confirmed in accordance with the device's label).

All sexually active male patients must agree to prevent potential transfer to and exposure of partner(s) to drug through ejaculate by using a condom consistently and correctly, beginning with the first dose of investigational product and continuing for at least 28 days after the last dose of bosutinib.

4.5. Sponsor's Qualified Medical Personnel

The contact information for the sponsor's appropriately qualified medical personnel for the trial is documented in the study contact list located in the Study Reference Manual.

To facilitate access to appropriately qualified medical personnel on study-related medical questions or problems, patients are provided with a contact card. The contact card contains, at a minimum, protocol and investigational product identifiers, patient study number, contact information for the investigator site and contact details for a contact center in the event that the investigator site staff cannot be reached to provide advice on a medical question or problem originating from another healthcare professional not involved in the patients participation in the study. The contact number can also be used by investigator staff if they are seeking advice on medical questions or problems, however it should only be used in the event that the established communication pathways between the investigator site and the study team are not available. It is therefore intended to augment, but not replace the established communication pathways between the investigator site and study team for advice on medical questions or problems that may arise during the study. The contact number is not intended for use by the patient directly and if a patient calls that number they will be directed back to the investigator site.

5. STUDY TREATMENTS

For the purposes of this study, and per International Conference on Harmonisation (ICH) guidelines, investigational product is defined as a pharmaceutical form of an active ingredient or placebo being tested or used as a reference/comparator in a clinical trial, including a product with a marketing authorization when used or assembled (formulated or packaged) in a way different from the approved form, or when used for an unapproved indication, or when used to gain further information about an approved use (ICH E6 1.33).

Starting dose of bosutinib therapy is 500 mg once daily (commercial formulation of 100 mg and 500 mg tablets provided), will be taken with food. Patients will be provided diary cards to record bosutinib administration, any adverse events that occur, and concomitant medications.

Bosutinib will be administered for at least 4 years from the date of first dose, unless treatment is discontinued early due to disease progression or unacceptable toxicity or other reasons outlined in [Section 5.3](#). Patients discontinuing bosutinib prior to at least 4 years on treatment will be followed for survival until the patient has completed at least 4 years on study (from time of first dose). Patients still deriving benefit from bosutinib at the time of study discontinuation may switch to commercially available product.

5.1. Allocation to Treatment

When registering a patient, an email should be sent to the study team indicating when screening is beginning, when screen failure occurs (if there is a screen failure), and when dosing occurs. For patients being treated with bosutinib, the information in the email should include the eligibility worksheet, enrollment form, and patient summary. Sites will use their 4-digit site number and assign a 4-digit patient number as follows:

- The patients in 2nd- or 3rd- line Ph+ [Chronic Phase (CP), Accelerated (AP), Blast Phase (BP)] CML patients (e.g. 12341001 – 1234 being the site number and 1001 being the first Ph+ patient screened) and continue patient assignments in ascending order for subsequent patients in this line of treatment.
- For patients with Ph+ CML $\geq 4^{\text{th}}$ -line Ph+ (CP, AP, BP) CML, the patient number will start with 2001 (e.g., 12342001) and subsequent assignments will continue in ascending order for patients in this line of treatment.
- For patients with Ph- CML, the patient number will start with 3001 (e.g. 12343001) and subsequent assignments will continue in ascending order for patients in this line of treatment.
- It is the investigator's determination if and when a patient meets criteria for enrollment.

5.2. Dose Modifications

The recommended starting bosutinib dosing has been defined as 500 mg once daily; however, the daily dose can vary as described in the table below:

Table 2. Available Dose Levels

Dose Level	Daily Bosutinib Dose
+1	600 mg ^a
0 (Starting Bosutinib Dose)	500 mg
-1	400 mg ^b
-2	300 mg ^{b,c}

a. The maximum dose escalation on study is 600 mg/day. Dose escalation to a dose greater than 600 mg is prohibited.

b. Once the dose has been reduced for a patient, the patient should remain on that dose unless an additional dose reduction is required or the dose is escalated as defined in the dose management instructions in case of toxicity (see Table 3 and Table 4 and relevant footnotes)

c. Consideration may be given to reducing bosutinib to 200 mg/day for CP CML patients who are not tolerating the 300 mg dose but otherwise benefiting from bosutinib. No dose reductions below 200 mg/day will be permitted. If the investigator and the Sponsor decide that it is not in the best interest of the patient to remain on treatment at a dose lower than 300 mg/day, the patient will be discontinued from treatment and will only be followed up for survival.

5.2.1. Bosutinib Dose Escalation

Patients will be allowed to dose escalate to 600 mg/day in the absence of any grade 3/4 or persistent grade 2 adverse drug reaction (or adverse event), if the response is unsatisfactory or there are signs of disease progression. These include, but are not limited to:

- Failure to achieve complete hematologic response (CHR) by Week 8.
- Failure to achieve complete cytogenetic response (CCyR) by Week 13 (Ph+ CML patients only).

If it is determined via qRT-PCR that a patient who has achieved a previous MMR while on study now has a rising level of BCR-ABL transcripts (5 times rise, accompanied with loss of MMR) the investigator should contact the Sponsor to determine if the patient's dose should be escalated to further optimize their response.

Dose escalation to a dose greater than 600 mg is prohibited.

5.2.2. Dose Adjustments for Adverse Reactions

Bosutinib dosing may be interrupted with or without dose reduction in case of treatment-related toxicity according to the guidelines described in the following tables. Dosing interruption and dose reduction is advised for the management of hematologic and non-hematologic adverse drug reactions. [Appendix 4](#) provides specific guidance to patients in the management of diarrhea.

Table 3. Non-Hematologic Treatment-Related Toxicity

Adverse Event Type and Severity	Action
Grade 1	Remain on current dose level.
Grade 2	For persistent clinically relevant toxicity not responding to optimal management: Interrupt bosutinib treatment, and reintroduce at the same dose or reduce dose by 1 level upon recovery to grade ≤ 1 within 4 weeks of stopping treatment.
Grade 3 ^a	For persistent clinically relevant toxicity not responding to optimal management: Interrupt bosutinib treatment, then dose reduce by 1 level upon recovery to grade ≤ 1 within 4 weeks of stopping treatment. If recovery takes longer than 4 weeks, the investigator should contact the sponsor to determine if the patient may continue on bosutinib.
Grade 4 ^a	Interrupt bosutinib treatment. Investigator and Sponsor to review to determine if patient may continue on bosutinib with appropriate dose reduction.
Specific AEs	
Elevated liver transaminases ^b	If elevations in liver transaminases $>5 \times$ institutional upper limit of normal (ULN) occur, bosutinib treatment should be interrupted until recovery to $\leq 2.5 \times$ ULN and may be resumed at 400 mg once daily thereafter. If recovery takes longer than 4 weeks, permanent discontinuation of bosutinib should be considered. If transaminase elevations $\geq 3 \times$ ULN occur concurrently with bilirubin elevations $>2 \times$ ULN and alkaline phosphatase $<2 \times$ ULN, bosutinib should be permanently discontinued.
Diarrhea	For Grade 3-4 diarrhea, bosutinib treatment should be interrupted and may be resumed at 400 mg once daily upon recovery to grade ≤ 1 . See Appendix 4 for further guidance on diarrhea management.
Renal	For Grade 3 renal impairment (CrCL 30 to 50 mL/min calculated by the Cockcroft-Gault formula), bosutinib treatment should be interrupted until recovery to Grade ≤ 1 , then may be resumed at 400 mg once daily. For Grade 4 renal impairment (CrCL <30 mL/min, calculated by the Cockcroft-Gault formula), bosutinib treatment should be interrupted until recovery to Grade ≤ 1 , then may be resumed at 300 mg once daily.

a. Treatment should only be reintroduced when all toxicities are Grade ≤ 1 and the treating physician feels it is in the patient's best interest. Pfizer must be notified by email that treatment has been restarted. For patients who have required a dose reduction due to toxicity, but then have been free of the specific toxicity (Grade ≤ 1) and are otherwise tolerating bosutinib well, the investigator may choose to re-escalate the dose by 1 dose level (if it is in the patient's best interest) until the patient is back to the starting or previous dose (whichever is higher). See Table 2 for available dose levels.

b. For patients with pre-existing liver transaminase baseline values above the normal range (ALT/AST $\leq 5 \times$ ULN if attributable to liver involvement of leukaemia) who subsequently present with AST or ALT ≥ 2 times the baseline values and ≥ 3 times the ULN, or ≥ 8 times the ULN (whichever is smaller), bosutinib should be interrupted until recovery to baseline levels.

Table 4. Hematologic Treatment-Related Toxicity

Adverse Event Severity	Action
Grade 1	Remain on current dose level
Grade 2	Remain on current dose level
Grade 3 ^{a, b}	Interrupt bosutinib treatment: If recovered to grade ≤ 2 within 2 weeks of treatment hold: re-introduce bosutinib at same dose. If recovered within 4 weeks of treatment hold: reduce bosutinib by one dose level. In case of recurrent grade 3 toxicity, dose must be reduced upon recovery to grade ≤ 2 . If recovery takes longer than 4 weeks, the investigator should contact the Sponsor to determine if the patient may continue on bosutinib.
Grade 4 ^a	Withhold bosutinib treatment. Investigator and Sponsor to review to determine if patient may continue on bosutinib with appropriate dose reduction.

a. For patients requiring dose reduction due to toxicity, who have been free of the toxicity (grade ≤ 1) and are otherwise tolerating bosutinib well, the investigator may choose to re-escalate the dose by 1 dose level (if it is in the patient's best interest) until the patient is back to the starting or previous dose (whichever is higher) – see Table 2 for available dose levels.

b. For AP and BP patients who enter the study with Grade 3 neutropenia or anemia due to underlying disease, bosutinib dose does not require dosing interruption/reduction, unless, in the opinion of the investigator, the Grade 3 event is due to bosutinib toxicity, in which case the bosutinib dosing guidelines should be followed. If neutropenia, thrombocytopenia and/or anemia worsen to grade 4, bosutinib dosing should be interrupted, with subsequent dose reduction. Any Grade 3 hematologic toxicity occurring after 4 or more weeks on treatment should be managed by interrupting/reducing bosutinib dosing as recommended.

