Symptomatic deterioration is a worsening of the disease under study that does not meet the definition of disease progression, but in the investigator's opinion, indicates the treatment is no longer effective and alternative therapeutic options should be undertaken, if dose escalation is not an option or has not been successful.

Dose escalations up to 600 mg daily dose are permitted for patients with unsatisfactory response or who show signs of disease progression and do not have concurrent grade 3 or 4 treatment related adverse events as described in [Section 5.2.1](#). The patient should be monitored closely to assess tolerability and any improvements in efficacy on the increased dose. If the patient's disease does not improve and/or continues to worsen, the patient should be permanently m bosutinib treatment.

4. Bosutinib treatment interruption for longer than 4 weeks due to treatment related toxicity, unless decided (and documented) otherwise by the investigator and Sponsor (see [Table 3](#) and [Table 4](#)).
5. Bosutinib dose reduction below 200 mg/day. No dose reductions below 200 mg/day will be permitted.
6. Withdrawal of consent.
7. Sponsor decision.
8. Pregnancy.
9. Death.

Survival follow-up information will be obtained for all patients who discontinue bosutinib treatment prior to completing at least 4 years of treatment from the time of first dose. See [Section 6.4](#) for detailed procedures.

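### Table 3's specific-toxicity rows name a fixed restart dose whatever the dose at onset, so a patient already reduced could restart unchanged or higher, contrary to the general rows

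*Protocol*

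**What the plan says.** Protocol Section 5.2 sets the dose ladder. "The recommended starting bosutinib dosing has been defined as 500 mg once daily" is level 0. Table 2 adds 600 mg as level +1 ("The maximum dose escalation on study is 600 mg/day"), 400 mg as level -1 and 300 mg as level -2. Footnote c adds a case-by-case option: "Consideration may be given to reducing bosutinib to 200 mg/day for CP CML patients who are not tolerating the 300 mg dose".

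Table 3 in Section 5.2.2 then has two kinds of rule for non-hematologic toxicity.

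- General rows, relative to the current dose. For Grade 3: "Interrupt bosutinib treatment, then dose reduce by 1 level upon recovery to grade" 1 or lower. For Grade 4: interruption, then a joint investigator and sponsor decision on continuing at a suitably reduced dose. No step size is named for Grade 4.
- Rows for specific events, in absolute doses. For Grade 3-4 diarrhea: "bosutinib treatment should be interrupted and may be resumed at 400 mg once daily upon recovery to grade" 1 or lower. Transaminases above 5 x ULN and Grade 3 renal impairment also restart at 400 mg, and Grade 4 renal impairment at 300 mg.

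Two footnotes bear on a patient already reduced. Table 2 footnote b says "Once the dose has been reduced for a patient, the patient should remain on that dose unless an additional dose reduction is required", but then excepts escalation made under the toxicity instructions of Tables 3 and 4. Table 3 footnote a, attached to the general Grade 3 and 4 rows, lets the investigator re-escalate by one level a patient who has been free of the toxicity and otherwise tolerates the drug.

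On escalation to 600 mg, Section 5.2.1 allows it "in the absence of any grade 3/4 or persistent grade 2 adverse drug reaction (or adverse event"). Section 5.3 allows it for patients who "do not have concurrent grade 3 or 4 treatment related adverse events as described in" Section 5.2.1.

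**The concern.** The specific rows read as if every patient were at or near the starting dose when the event occurs. The protocol expects otherwise, since it provides five possible daily doses. For a patient already reduced, the named restart dose can equal or exceed the dose on which a serious toxicity arose. The general rows point the other way, and no text says which kind of row takes precedence or what happens when they disagree.

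What is at stake is mainly patient safety and uniform conduct: two sites could follow the protocol and restart the same patient at different doses. The SAP's descriptive summaries would carry that variation, for example dose received over time (Section 8.2.4.2) and adverse events before and after the initial reduction to 400, 300 and 200 mg (Section 8.2.4.8). The primary endpoint definition is not touched, and the SAP has no hypothesis test to affect.

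**Working it through.** The plan gives no figure to reproduce here. The check sets each fixed restart dose beside one level down for every dose a patient can be on.

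Inputs: doses of 600, 500, 400 and 300 mg from Table 2, and 200 mg from its footnote c (chronic phase only); fixed restarts of 400 mg (transaminases, Grade 3-4 diarrhea, Grade 3 renal) and 300 mg (Grade 4 renal) from Table 3. Change = restart dose minus dose at onset.

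| Dose at onset | One level down | 400 mg rows | 300 mg row |
|---|---|---|---|
| 600 mg | 500 mg | 400 - 600 = -200 mg (two levels down) | 300 - 600 = -300 mg (three levels down) |
| 500 mg | 400 mg | 400 - 500 = -100 mg (one level, agrees) | 300 - 500 = -200 mg (two levels down) |
| 400 mg | 300 mg | 400 - 400 = 0 (unchanged) | 300 - 400 = -100 mg (one level, agrees) |
| 300 mg | 200 mg, chronic phase option only | 400 - 300 = +100 mg (higher) | 300 - 300 = 0 (unchanged) |
| 200 mg | none permitted | 400 - 200 = +200 mg (higher) | 300 - 200 = +100 mg (higher) |

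Each fixed dose equals one level down at one of the five doses: 500 mg for the 400 mg rows and 400 mg for the 300 mg row. The cells that matter are those showing no change or an increase: three of five for the 400 mg rows and two of five for the 300 mg row. The larger reductions from 600 or 500 mg are not counted as conflicts, because a row for a specific event may reasonably ask for more than the general row.

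The comparison row depends on grade. For Grade 3 diarrhea and Grade 3 renal impairment it is the one-level reduction. For Grade 4 diarrhea and Grade 4 renal impairment it is the joint review with a reduction of unstated size. An unchanged or higher restart fits neither, and the specific rows do not mention the joint review. The transaminase row is defined by a multiple of ULN rather than a grade, so setting it against the general Grade 3 row is an assumption.

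Do the footnotes settle it?

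- Table 2 footnote b would hold a reduced patient at the reduced dose, but its exception sends the reader back to Tables 3 and 4, where the disagreement lies. Even without the exception, staying at 400 mg is not a reduction.
- Table 3 footnote a limits re-escalation to one level and requires that the patient has been free of the toxicity. A restart from 200 to 400 mg exceeds one level. Restarts from 300 to 400 mg or from 200 to 300 mg are one step in size, but the specific rows attach them to recovery itself, without that footnote's tolerability condition.

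Escalation wording: Section 5.2.1 covers grade 3/4 and persistent grade 2 reactions and adds adverse events in a parenthesis. Section 5.3 covers only concurrent, treatment-related grade 3 or 4 events. A patient with a persistent grade 2 reaction is excluded by the first and not by the second.

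**The case against.** The strongest reply is that rows for specific events are meant to differ from general rows, so a difference alone is no contradiction. The restart wording is permissive, the tables are described as guidelines, and footnote b tells sites to leave reduced patients where they are. The general Grade 3 row is itself limited to persistent, clinically relevant toxicity that does not respond to management. A sensible investigator would not raise the dose after Grade 3-4 diarrhea.

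Much of this stands, and it narrows the point. It disposes of the 600 mg cells. It does not dispose of the others: resuming is optional, but the only dose named is the fixed one, and footnote b's exception leads back to the same table.

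Some stronger readings are tempting but not supported.

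- A reader might infer that the rules agree only at 500 mg. That is true of the 400 mg rows but not of Grade 4 renal impairment, where the match is at 400 mg.
- A reader might treat one level down as the general rule for every serious event. It is not the Grade 4 rule.
- A reader might take the 43% of bosutinib patients with dose reductions in the Phase 3 background study (Protocol Section 1.2.2) as the share affected. That study enrolled newly diagnosed patients, and the figure counts any reduction. The conflict needs a patient at a particular dose who then has one of the named events.
- A reader might see Sections 5.2.1 and 5.3 as rival escalation rules. Section 5.3 cites Section 5.2.1 as its source, so it reads as a loose restatement.
- A reader might expect the successful rechallenge summary to be distorted by definition. SAP Section 6.2.8 defines it by re-dosing after a delay without discontinuing for that event; the restart dose does not enter.

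**Conclusion.** The inconsistency is real and limited. Followed literally, the specific rows produce an unchanged restart at 400 mg (300 mg for Grade 4 renal impairment) and a higher restart below that, and the general rows contradict both outcomes. No footnote resolves it. This rests on reading the specific rows as written, without an implied condition on the dose at onset, and on counting 200 mg as a possible current dose in chronic phase only.

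Its frequency cannot be stated, because the documents give no rate for a second, specific toxicity in a patient already at a reduced dose. It should be corrected because it concerns re-exposure after serious toxicity and the remedy is cheap, not because it threatens the efficacy analysis. The escalation mismatch is a minor wording point. Nothing here implies a view on which restart dose or escalation condition is right.

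**What to change.** Reconcile the specific rows of Table 3, its general Grade 3 and Grade 4 rows, Table 3 footnote a and Table 2 footnote b, so that a site finds one instruction for each event at every dose the patient may be on. The text should say which kind of row takes precedence, and whether the joint investigator and sponsor review applies to Grade 4 diarrhea and Grade 4 renal impairment. Make Sections 5.2.1 and 5.3 state the same escalation condition. The content of each rule is for the sponsor's clinicians.

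The cost is protocol wording, by clarification letter or amendment. Sample size, endpoints and planned analyses do not change. A late correction would reach fewer patients: SAP Section 8.2.2 reports that more than 80% were off treatment by 11 March 2020.
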